4.6.1.1. Oseltamivir Risk Assessment

Specific information regarding warnings, precautions, contraindications, adverse events, and other pertinent information is available in the local product label for oseltamivir.

Currently, there are no drugs that have demonstrated clinical efficacy in randomized clinical trials in the hospitalized influenza population. Twice daily 75 mg OSV is approved for treatment of uncomplicated acute influenza and is recommended for treatment in the hospitalized population, in the Infectious Diseases Society of America guidelines [Harper, 2009], guidelines from Centers for Disease Control and Prevention [CDC, 2011] and World Health Organization [WHO, 2010]. In the on-going Study 201682, oral 75 mg DNX and 75 mg OSV were co-administered to subjects with uncomplicated influenza, with no safety concerns identified to date.

4.6.2. Benefit Assessment

Currently, there is an unmet medical need for more effective treatments of viral lower respiratory tract infections (LRTI) requiring hospitalization. This study will provide an opportunity to determine if an anti-inflammatory drug with a novel mode of action may offer clinical benefit for the treatment of hospitalized influenza. This study follows an ongoing study of DNX alone or in combination with OSV in subjects with acute, uncomplicated influenza where no concerns have been identified to date.

In Phase I clinical trials to date and also in a phase IIa study in subjects with mild influenza who had co-administered OSV, all AEs (e.g. the most commonly observed AEs are headache and diarrhea) were mild-to-moderate in intensity in healthy subjects. In this study, the efficacy and safety of DNX co-administered with OSV will be evaluated in subjects hospitalized for influenza infections.

4.6.3. Overall Benefit:Risk Conclusion

Taking into account the measures taken to minimize risk to patients participating in this Phase II clinical trial, the potential risks identified in association with GSK1325756/DNX are justified by the anticipated benefits that may be afforded to patients with severe viral respiratory tract infections.

5. SELECTION OF STUDY POPULATION AND WITHDRAWAL CRITERIA

Specific information regarding warnings, precautions, contraindications, adverse events, and other pertinent information on the GSK investigational product or other study treatment that may impact subject eligibility is provided in the Investigator's Brochure 2016; and oseltamivir prescribing information.

Written informed consent must be obtained from each potentially eligible subject or by an LAR for subjects who are incapable of consenting themselves such as those who are unconscious or due to their medical condition (e.g. too weak or debilitated, severe shortness of breath), prior to the initiation of any study procedures as outlined in this protocol. The consent form must have been approved by the Institutional Review

Board/Independent Ethics Committee (IRB/IEC). After signing an informed consent, subjects will complete assessments to determine subject eligibility. Each subject being evaluated for study enrollment will be assigned a subject number. This number will be given sequentially in chronological order of subject presentation according to a numeric roster provided by GSK.

Deviations from inclusion and exclusion criteria are not allowed because they can potentially jeopardize the scientific integrity of the study, regulatory acceptability or subject safety. Therefore, adherence to the criteria as specified in the protocol is essential.

5.1. Inclusion Criteria

A subject will be eligible for inclusion in this study only if all of the following criteria apply:

AGE
1. Adults 18 years (as per local laws) of age and older at the time of signing the informed consent.
TYPE OF SUBJECT AND DIAGNOSIS INCLUDING DISEASE SEVERITY

2. Presence of fever ($\geq 38.0^{\circ}\text{C}$ [$\geq 100.4^{\circ}\text{F}$] by any route) at Baseline (enrollment) or history of fever/feverishness during the 48 hours prior.
 
3. O_2 saturation $< 95\%$ on room air by trans-cutaneous method OR need for any supplemental oxygenation (non-invasive ventilation, facemask, facetent, nasal canula, etc) or ventilator support (mechanical ventilation, bi-level positive airway pressure [BIPAP], continuous positive airway pressure [CPAP]) or increase in oxygen supplementation requirement of ≥ 2 liters for subjects with chronic oxygen dependency. For those subjects with a history of chronic hypoxia (without supplemental oxygen), an oxygen saturation of at least 3% below the subject's historical baseline oxygen saturation.
 
AND AT LEAST 2 out of the following 3:
 
 • Respiratory rate > 24 breaths per minute. For those subjects who require ventilator support or oxygen supplementation, this requirement is waived. • Heart rate > 100 bpm • Systolic bp < 90 mm Hg. 
4. Severity of symptoms at enrollment:
 
 • Less severe hospitalized subjects are those who (but not limited to): 
 • are hemodynamically stable; • may require oxygenation with facemask, facetent, nasal canula, etc; • may or may not have radiological signs of lower respiratory tract disease; or • have exacerbation of underlying chronic disease, including asthma, chronic

obstructive pulmonary disease (COPD), or other cardiovascular conditions not leading to hemodynamic compromise.

- Critically ill hospitalized subjects are those who (but not limited to):
 - require CPAP, BIPAP, mechanical ventilation;
 - have hemodynamic instability (with or without pressor support); or
 - have central nervous system involvement (eg encephalopathy, encephalitis).
- 5. Presence of influenza that in the Investigator's judgment requires hospitalization for treatment and supportive care
- 6. Onset of influenza symptoms within 6 days prior to study enrolment. Symptoms may include cough, dyspnea, sore throat, feverishness, myalgias, headache, nasal symptoms (rhinorrhea, congestion), fatigue, diarrhea, nausea and vomiting.
- 7. A positive result from a rapid influenza test (provided by GSK) or other available, local laboratory diagnostic test;
- 8. Baseline renal criteria as follows:

Sentinel Cohorts:

- Normal renal function: Baseline creatinine clearance within normal reference ranges (≥ 80 mL/min) for the first approximately 30 subjects enrolled;
- Mild renal impairment: Baseline creatinine clearance of 50-79 mL/min for the next approximately 10 subjects enrolled into the sentinel cohort;
- Moderate renal impairment: Baseline creatinine clearance of 30-49 mL/min for the next approximately 10 subjects enrolled into the sentinel cohort.

Post-sentinel cohorts:

- Normal renal function, mild or moderate renal impairment: creatinine clearance > 30 mL/min.

9. Baseline Liver Function Tests as follows:

Liver parameter	ALT \leq 5xULN	ALT $>$ 5 and \leq 8xULN	ALT $>$ 8xULN
Bilirubin \leq 2x ULN	Include	Include only if bilirubin $<$ 1.5xULN	Exclude
Bilirubin $>$ 2x ULN	Exclude	Exclude	Exclude

SEX

10. Male or Female subjects could be eligible if :

Males:

Male subjects with female partners of child bearing potential must comply with the

following contraception requirements from the time of first dose of study medication until at least 36 hours (five half-lives) after the last dose of study medication.

- a. Vasectomy with documentation of azoospermia.
- b. Male condom plus partner use of one of the contraceptive options below:
 - Contraceptive subdermal implant
 - Intrauterine device or intrauterine system
 - Oral Contraceptive, either combined or progestogen alone [[Hatcher, 2007a](#)]
Injectable progestogen [[Hatcher, 2007a](#)]
 - Contraceptive vaginal ring [[Hatcher, 2007a](#)]
 - Percutaneous contraceptive patches [[Hatcher, 2007a](#)]

This is an all-inclusive list of those methods that meet the following GSK definition of highly effective: having a failure rate of less than 1% per year when used consistently and correctly and, when applicable, in accordance with the product label. For non-product methods (e.g., male sterility), the investigator determines what is consistent and correct use. The GSK definition is based on the definition provided by the ICH [[ICH, M3 \(R2\) 2009](#)].”

The investigator is responsible for ensuring that subjects understand how to properly use these methods of contraception.

Females:

- a. Non-reproductive potential defined as:
 - Pre-menopausal females with one of the following:
 - Documented tubal ligation
 - Documented hysteroscopic tubal occlusion procedure with follow-up confirmation of bilateral tubal occlusion
 - Hysterectomy
 - Documented Bilateral Oophorectomy
- b. Postmenopausal defined as 12 months of spontaneous amenorrhea [in questionable cases a blood sample with simultaneous follicle stimulating hormone (FSH) and estradiol levels consistent with menopause (refer to laboratory reference ranges for confirmatory levels)]. Females on hormone replacement therapy (HRT) and whose menopausal status is in doubt will be required to use one of the highly effective contraception methods if they wish to continue their HRT during the study. Otherwise, they must discontinue HRT to allow confirmation of post-menopausal status prior to study enrolment.
- c. Reproductive potential and agrees to follow one of the options listed in the Modified List of Highly Effective Methods for Avoiding Pregnancy in Females of Reproductive Potential (FRP) (see [Appendix 6](#)) from the first dose of study medication until at least 36 hrs after the last dose of study medication and completion

of the PT Day 3 visit.

The investigator is responsible for ensuring that subjects understand how to properly use these methods of contraception.

INFORMED CONSENT

11. Subjects willing and able to give written informed consent to participate in the study and to adhere to the procedures stated in the protocol OR Legally acceptable representative (LAR) willing and able to give written informed consent on behalf of the subject to participate in the study for unconscious adults, and those incapable of consenting themselves due to their medical condition (e.g. too weak or debilitated, severe shortness of breath), due to literacy issues or included as permitted by local regulatory authorities, IRB/IECs or local laws.

COUNTRY-SPECIFIC

12. French subjects: In France, a subject will be eligible for inclusion in this study only if either affiliated to or a beneficiary of a social security category.

5.2. Exclusion Criteria

A subject will not be eligible for inclusion in this study if any of the following criteria apply:

CONCURRENT CONDITIONS/MEDICAL HISTORY (INCLUDES LIVER FUNCTION AND QTc INTERVAL)

1. Subjects who, in the opinion of the investigator, are not likely to survive the next 48 hours beyond Baseline;
2. Immunosuppression, whether due to primary immunosuppressive conditions, such as history of inherited immunodeficiency syndromes, HIV infection, or secondary conditions, such as immunosuppressive medication, stem cell or solid organ transplantation, or malignancy;
3. Documented current liver disease (including Hepatitis A, B, or C), or known hepatic or biliary abnormalities (with the exception of Gilbert's syndrome or asymptomatic gallstones);
4. QTc Criteria: QTcB or QTcF >480 msec or >500 msec with bundle branch block;
5. For subjects enrolled in the sentinel cohorts: diabetes mellitus and chronic kidney disease;
6. Subjects who require dialysis, or are on renal replacement therapies;
7. Subjects who require extra corporeal membrane oxygenation (ECMO) at baseline (enrolled subjects who subsequently require ECMO may continue in the study)
8. Women who are pregnant as determined by a positive human chorionic gonadotrophin (hCG) ultrasensitive test prior to dosing or women who are

breastfeeding;

CONCOMITANT MEDICATIONS

9. Subjects who received other treatments for influenza including vitaglutam, umifenovir, and neuraminidase inhibitors (oseltamivir, zanamivir, peramivir) for more than 72 hours during current acute illness;
10. Subjects who received any immunoglobulins within 6 months of screening or planned administration of any of these products during the treatment period.
11. Subjects treated with cytotoxic or immunosuppressive drugs within six months of study enrolment. Topical, intra-articularly injected, or inhaled glucocorticoids, topical calcineurin inhibitors or imiquimod are allowed.

RELEVANT HABITS

12. Known history of drug abuse within 6 months of study start.

CONTRAINDICATIONS

13. History of sensitivity to any of the study medications, or components thereof or a history of drug or other allergy that, in the opinion of the investigator or Medical Monitor, contraindicates their participation.

DIAGNOSTIC ASSESSMENTS AND OTHER CRITERIA

14. Absolute neutrophil count <1.0 Gi/L
15. Subjects who have participated in a clinical trial using an investigational product within the following time period prior to the first dosing day in the current study: 30 days, 5 half-lives or twice the duration of the biological effect of the investigational product (whichever is longer).

5.3. Screening/Baseline/Run-in Failures

Screen failures are defined as subjects who consent to participate in the clinical trial but are never subsequently randomized. In order to ensure transparent reporting of screen failure subjects, meet the Consolidated Standards of Reporting Trials (CONSORT) publishing requirements, and respond to queries from Regulatory authorities, a minimal set of screen failure information is required including Demography, Screen Failure details, Eligibility Criteria, and Serious Adverse Events (see Section 7.4.1.6).

5.4. Withdrawal/Stopping Criteria

A subject is considered to be withdrawn prematurely from the study if they do not complete the Day 45 Visit.

Criteria for premature study withdrawal include:

- Adverse event
- protocol deviation
- non-compliance
- subject lost to follow up
- subject withdraws consent
- investigator discretion
- sponsor terminates the study

The following actions must be taken in relation to a subject who fails to attend the clinic for a required study visit:

- The site must attempt to contact the subject and re-schedule the missed visit as soon as possible.
- The site must counsel the subject on the importance of maintaining the assigned visit schedule and ascertain whether or not the subject wishes to and/or should continue in the study.
- In cases where the subject is deemed ‘lost to follow up’, the investigator or designee must make every effort to regain contact with the subject (where possible, 3 telephone calls and if necessary a certified letter to the subject’s last known mailing address or local equivalent methods). These contact attempts should be documented in the subject’s medical record.
- Should the subject continue to be unreachable, only then will he/she be considered to have withdrawn from the study with a primary reason of “Lost to Follow-up”.

A subject may withdraw from study treatment at any time at his/her own request, or may be withdrawn at any time at the discretion of the investigator for safety, behavioral or administrative reasons. If a subject withdraws from the study, he/she may request destruction of any samples taken, and the investigator must document this in the site study records.

5.4.1. Premature Discontinuation of Investigational Product

A subject is considered to have prematurely discontinued investigational product (IP) if they have not completed 5 days of randomized treatment (not applicable for subjects discharged from the hospital due to symptom improvement).

If a subject is prematurely discontinued from IP, the investigator must make every effort to perform all the remaining study visits as described in the Time and Events Table, including the final Day 45 Visit.

5.4.2. Liver Chemistry Stopping Criteria

Liver chemistry stopping and increased monitoring criteria have been designed to assure subject safety and evaluate liver event etiology (in alignment with the FDA premarketing clinical liver safety guidance).

<http://www.fda.gov/downloads/Drugs/GuidanceComplianceRegulatoryInformation/Guidances/UCM174090.pdf>

If any of the stopping criteria for parameters below are observed and confirmed, cessation of drug dosing and further evaluations will be instituted.

Liver Parameter	ALT \leq 10xULN	ALT >10xULN
Bilirubin \leq 2xULN	Continue	Discontinue IP
Bilirubin >2xULN (>35% direct)	Discontinue IP if ALT >5xULN, report as an SAE	Discontinue IP, report as an SAE

Study Treatment Restart or Rechallenge

Study treatment restart or rechallenge after liver chemistry stopping criteria are met by any subject participating in this study is not allowed.

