5.4.3. Corrected QT Interval (QTc) Stopping Criteria

- The *same* QT correction formula *must* be used for *each individual subject* to determine eligibility for and withdrawal from the study. This formula may not be changed or substituted once the subject has been enrolled.
 - For example, if a subject is eligible for the protocol based on QTcB, then QTcB must be used for withdrawal of this individual subject as well.
 - Once the QT correction formula has been chosen for a subject's eligibility, the *same formula* must continue to be used for that subject *for all QTc data being collected for data analysis*. Safety electrocardiograms (ECGs) and other non-protocol specified ECGs are an exception.

- The QTc stopping criteria should be based on averaged QTc values of triplicate electrocardiograms obtained over a brief (e.g., 5-10 minute) recording period.

A subject who meets either of the bulleted criteria below will be permanently discontinued from IP:

- QTc >530 msec
- Increase in QTcF or QTcB by more than 60 msec compared to baseline on two separate ECG tracings.

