5.4.4. Other Stopping Criteria

Subjects should be permanently discontinued from IP if any of the following conditions are met:

- Serum creatinine: 0.5 mg/dL increase from baseline, on 2 successive readings;
- eGFR of <60 on two consecutive readings using the CKD-EPI calculation (eGFR of <30 for moderate renal impairment);
- Peripheral neutropenia: absolute neutrophil counts <0.5 Gi/L on 2 successive assessments.

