		Baseline/ Study Day 1 ^a	Study Day 2	Study Day 3	Study Day 4	Study Day 5 /day of last dose ^a	Study Day 6 if applicable ^b	
Study Treatments								
Administration of investigational medication (IV) and oseltamivir (oral) twice daily		X	X	X	X	X	X	

- a. A 'Day' is defined as a 24 hour period (Treatment Day), therefore depending on the start time of the first dose of IV DNX, a Treatment Day may span two calendar days.
- b. Day 6 assessments only applicable if last day of dose of randomized treatment is on Day 6 (i.e for subjects who received first dose after 12 noon on Baseline/Day 1.
- c. Physical exam to be performed twice daily for subjects in the sentine cohort.
- d. Enrollment into the study will be based on history of diagnosis of HIV and liver disease. Blood samples will be analyzed after enrollment to retrospectively determine if subject is HIV, Hep B or Hep C positive; however, results will not be available until after completion of dosing.
- e. Influenza symptoms to be assessed only at baseline for inclusion.
- f. Enrollment into the study will be based on any history of diagnosis of HIV and liver disease.
- g. Chest X-ray at Baseline and whenever clinically indicated.
- h. ECG: For the ECG on Baseline/Day 1, one 12-lead ECG (can be done within approximately 24 hours prior to dosing). At Baseline and on Day 5 or last treatment day, a monitoring strip can be utilized if a 12-lead ECG cannot be performed.
- i. Concomitant medications for influenza treatment of the current episode to be recorded from Day -7 (i.e. one week prior to baseline), if available.
- j. Complications of influenza such as bacterial pneumonia, pneumothorax, pleural effusion, ARDS, myositis, encephalitis, myocarditis, and associated antibiotic use will be recorded on all assessment days.
- k. Vital signs and ventilation status to be assessed three times daily during the treatment period between approximately 8 AM and 8 PM.
- l. Katz ADL score collected once daily while hospitalized.
- m. Activity level to be recorded as one of three responses (bed rest, limited ambulation or unrestricted) everyday while hospitalized
- n. Chemistry panel including Liver Function Tests to be required once every other day during treatment (local testing (L) of LFTs for subject management as well as central laboratory testing (C)).

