12.2. Appendix 2: Liver Safety Required Actions and Follow up Assessments

Phase II liver chemistry stopping and increased monitoring criteria have been designed to assure subject safety and evaluate liver event etiology (in alignment with the FDA premarketing clinical liver safety guidance).

<http://www.fda.gov/downloads/Drugs/GuidanceComplianceRegulatoryInformation/Guidances/UCM174090.pdf>.

Phase II Liver Chemistry Stopping Criteria

Liver Parameter	ALT \leq 10xULN	ALT >10xULN
Bilirubin \leq 2xULN	Continue	Discontinue IP
Bilirubin >2xULN (>35% direct)	Discontinue IP if ALT >5xULN, report as an SAE	Discontinue IP, report as an SAE

Required Actions and Follow-up Assessments to Liver Stopping Criteria

Required Actions and Follow up Assessments following ANY Liver Stopping Event	
Actions	Follow Up Assessments

 • Immediately discontinue study treatment • Report the event to GSK within 24 hours • Complete the liver event CRF and complete an SAE data collection tool if the event also meets the criteria for an SAE² • Perform liver event follow up assessments • Monitor the subject until liver chemistries resolve, stabilize, or return to within baseline (see MONITORING below) • Do not restart/rechallenge subject with study treatment. Permanently discontinue study treatment and may continue subject in the study for any protocol specified follow up assessments 	
 • Viral hepatitis serology⁴ • Blood sample for pharmacokinetic (PK) analysis, obtained 3 days after last dose⁵ • Serum creatine phosphokinase (CPK) and lactate dehydrogenase (LDH). • Fractionate bilirubin, if total bilirubin \geq2xULN • Obtain complete blood count with differential to assess eosinophilia • Record the appearance or worsening of clinical symptoms of liver injury, or hypersensitivity, on the AE report form • Record use of concomitant medications on the concomitant medications report form including acetaminophen, herbal remedies, other over the counter medications. • Record alcohol use on the liver event

Required Actions and Follow up Assessments following ANY Liver Stopping Event	
Actions	Follow Up Assessments

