
MONITORING:
 
For bilirubin or INR criteria:
 
 Repeat liver chemistries (include ALT, AST, alkaline phosphatase, bilirubin) and perform liver event follow up assessments within 24 hrs Monitor subjects twice weekly until liver chemistries resolve, stabilize or return to within baseline A specialist or hepatology consultation is recommended 
For All other criteria:
 
 Repeat liver chemistries (include ALT, AST, alkaline phosphatase, bilirubin) and perform liver event follow up assessments within 24-72 hrs Monitor subjects weekly until liver chemistries resolve, stabilize or return to within baseline 	
alcohol intake case report form
 
For bilirubin or INR criteria:
 
 Anti-nuclear antibody, anti-smooth muscle antibody, Type 1 anti-liver kidney microsomal antibodies, and quantitative total immunoglobulin G (IgG or gamma globulins). Serum acetaminophen adduct high performance liquid chromatography (HPLC) assay (quantifies potential acetaminophen contribution to liver injury in subjects with definite or likely acetaminophen use in the preceding week) [James, 2009]. Liver imaging (ultrasound, magnetic resonance, or computerised tomography) and /or liver biopsy to evaluate liver disease: complete Liver Imaging and/or Liver Biopsy CRF forms.

- Serum bilirubin fractionation should be performed if testing is available. If serum bilirubin fractionation is not immediately available, discontinue study treatment for that subject if ALT > 5x upper limit of normal (ULN). Additionally, if serum bilirubin fractionation testing is unavailable, **record presence of detectable urinary bilirubin on dipstick**, indicating direct bilirubin elevations and suggesting liver injury.
- All events of ALT > 5xULN **and** bilirubin ≥ 2xULN (>35% direct bilirubin), **must be reported as an SAE (excluding studies of hepatic impairment or cirrhosis)**; INR measurement is not required and the threshold value stated will not apply to subjects receiving anticoagulants
- New or worsening symptoms believed to be related to liver injury (such as fatigue, nausea, vomiting, right upper quadrant pain or tenderness, or jaundice) or believed to be related to hypersensitivity (such as fever, rash or eosinophilia)

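### Section 5.4.2 stops IP for a liver criterion only once it is confirmed, without defining confirmation or an interim hold, while Appendix 2 calls for immediate discontinuation

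*Protocol*

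**What the plan says.** Protocol section 5.4.2 gives a two-by-two table. IP is discontinued at ALT >10xULN, or at ALT >5xULN when bilirubin is >2xULN (>35% direct). The sentence that puts the table into effect reads: "If any of the stopping criteria for parameters below are observed and confirmed, cessation of drug dosing and further evaluations will be instituted". The section then closes the way back: "Study treatment restart or rechallenge after liver chemistry stopping criteria are met by any subject participating in this study is not allowed".

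Appendix 2 (section 12.2) prints the same table. Its list of actions after any liver stopping event begins "Immediately discontinue study treatment". Repeat chemistry comes under monitoring: within 24 h for bilirubin or INR criteria, and for all other criteria sites repeat the chemistry and "perform liver event follow up assessments within 24-72 hrs". A note on missing bilirubin fractions says: "If serum bilirubin fractionation is not immediately available, discontinue study treatment for that subject if ALT" exceeds 5xULN.

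Other stopping rules that ask for a second reading say what it is. For QTc change (5.4.3): "Increase in QTcF or QTcB by more than 60 msec compared to baseline on two separate ECG tracings". For creatinine (5.4.4): "Serum creatinine: 0.5 mg/dL increase from baseline, on 2 successive readings". The eGFR and neutrophil rules in 5.4.4 also name two consecutive or successive readings.

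On sampling, note n of the Time and Events Table (7.1) says: "Chemistry panel including Liver Function Tests to be required once every other day during treatment".

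**The concern.** The protocol states one safety rule twice, and the two statements need not lead to the same action. Read literally, 5.4.2 lets dosing continue after a first value above threshold until something undefined confirms it. Appendix 2 allows no further dose.

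The restart ban makes the choice consequential in both directions. A site that follows 5.4.2 may infuse drug at a value that the protocol itself treats as a reason to stop. A site that follows Appendix 2 ends treatment irreversibly on one result, even if the repeat is normal. An investigator who simply holds a dose pending a repeat cannot tell whether resuming would count as a barred restart, because 5.4.2 does not say whether a criterion is met at first observation or at confirmation.

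A subject may also enter close to a threshold. Inclusion criterion 9 admits ALT up to 8xULN if bilirubin is below 1.5xULN, and ALT up to 5xULN with bilirubin up to 2xULN.

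**Working it through.** The plan gives no figure to reproduce, so the check is a comparison of texts followed by a dose count.

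**1. The two statements side by side**

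| Question | Section 5.4.2 | Appendix 2 |
|---|---|---|
| Thresholds | ALT >10xULN; ALT >5xULN with bilirubin >2xULN (>35% direct) | Same table |
| When does IP stop? | When the criterion is observed and confirmed | Immediately, after any liver stopping event |
| What confirms it? | Not stated | No confirmation step |
| Is IP held meanwhile? | Not stated | Does not arise |
| Repeat chemistry | Not mentioned | Monitoring after the event: within 24 h, or 24 to 72 h |
| Restart | Not allowed | Not allowed |
| Reference to the other text | None to Appendix 2 | None to 5.4.2 |

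**2. Is confirmation defined anywhere else?**
- Section 7.4.6 asks for clinically significant abnormal values to be repeated until they return to normal or baseline. It sets no deadline and does not link the repeat to stopping.
- Section 7.4.6 also has LFTs run at the local laboratory for subject management, so a quick repeat is feasible.
- Table 7, footnote a, sends the reader to Appendix 2 for details of the liver stopping criteria.
- The SAP lists subjects with liver stopping events (Listing 24) without saying whether an unconfirmed value counts.

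None of these defines confirmation or an interim hold.

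**3. Doses at issue**

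Inputs: infusions about 12 h apart (6.1.1.3); treatment for up to 5 days (4.2), twice daily, so at most 5 × 2 = 10 doses. The wait is an assumption, because the protocol states none.

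Further doses ≈ wait ÷ 12 h, if dosing continues during the wait.

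- Appendix 2, immediate stop: 0 doses.
- Same-day local repeat (wait up to 12 h): 0 to 1 dose.
- Assumed 24 h wait: 24 ÷ 12 = 2 doses.

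The same arithmetic gives the cost of holding IP instead: a 24 h hold omits up to about 2 of 10 doses.

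**The case against.** The strongest reply is that a site would normally reach Appendix 2, because Table 7 footnote a names it as the place for details, and would then stop at once. The two texts can also be read in sequence: 5.4.2 says when a stopping event exists, and Appendix 2 says what to do after it. Both points carry weight. They make continued dosing the less likely reading, and a reader who infers a flat contradiction goes further than the documents do. But no text says that the Appendix 2 event is already a confirmed one. If it is, confirmation is still undefined; if it is not, the condition in 5.4.2 has no function.

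A reader might also infer that the liver rule alone lacks a deadline and a hold. It does not: the QTc, creatinine, eGFR and neutrophil rules give neither. What is specific to the liver rule is that it asks for confirmation without saying what it consists of, and that it sits beside a second text calling for an immediate stop.

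The fractionation note is weak evidence either way. It deals with a missing component of the bilirubin criterion, not with repeating a value.

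Finally, local LFTs, the repeat-test instruction and the investigator's freedom under 5.4 to withdraw a subject from treatment for safety all reduce the practical risk. They rest on individual judgement, which a stopping rule is meant to standardise.

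**Conclusion.** The point holds as a defect in how a safety rule is written, and it should be corrected. Section 5.4.2 and Appendix 2 do not give sites one instruction for a first liver value above threshold, and the restart ban makes the difference matter.

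The size is modest: 0 to 1 extra dose with a same-day local repeat and about 2 with an assumed 24 h wait, out of at most 10, against 0 under Appendix 2. These counts assume that dosing continues during the wait and that doses are 12 h apart.

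A reader might infer larger numbers, and the documents do not support them. Waiting for the next scheduled panel, 48 h later, would give 48 ÷ 12 = 4 doses, but only if no unscheduled repeat were done, which 7.4.6 makes unlikely. Expressing the extra doses as a share of those remaining on Day 3 or Day 5 would need the sample's timing relative to the infusion and the time to a result, and the protocol states neither. The 24 to 72 h window in Appendix 2 runs after discontinuation, so it is not a confirmation period.

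The SAP records that the study ended after 10 subjects were enrolled, so actual exposure to this ambiguity was small.

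**What to change.** Put the same rule in 5.4.2 and Appendix 2, and have each section refer to the other:

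- Hold IP as soon as a local value meets any criterion in the table.
- Repeat liver chemistry at the local laboratory within 24 h.
- If the repeat meets a criterion, or no repeat result is available by then, discontinue IP permanently.
- If the repeat does not meet a criterion, IP may resume at the next scheduled dose. State that this is not a restart or rechallenge, and that held doses are not made up.
- Keep the Appendix 2 note on unavailable bilirubin fractionation.

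The cost is protocol wording, one unscheduled local LFT per event, and up to about 2 missed doses for a subject whose value is not confirmed. The rule also relaxes the immediate permanent stop in Appendix 2, so the sponsor should adopt it deliberately.

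If the sponsor prefers the stricter policy, the minimal change is to delete the confirmation condition from 5.4.2 and refer there to Appendix 2. That removes the conflict, but leaves a permanent stop on a single value.
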